16.0 MULTICENTER REGULATORY REQUIREMENTS

Washington University requires that each participating site sends its informed consent document to be reviewed and approved by the Washington University Regulatory Coordinator (or designee) prior to IRB/IEC submission.

Site activation is defined as when the secondary site has received official written documentation from the coordinating center that the site has been approved to begin enrollment. At a minimum, each participating institution must have the following documents on file at Washington University prior to study activation:

- Documentation of IRB approval of the study in the form of a letter or other official document from the participating institution's IRB. This documentation must show which version of the protocol was approved by the IRB.
- Documentation of IRB approval of an informed consent form. The consent must include a statement that data will be shared with Washington University, including the Quality Assurance and Safety Monitoring Committee (QASMC), the DSMC (if applicable), and the Washington University study team.
- Documentation of FWA, signed FDA Form 1572 (if applicable), and the CVs of all participating investigators.
- Protocol signature page signed and dated by the investigator at each participating site.

The coordinating center Principal Investigator (or designee) is responsible for disseminating to the participating sites all study updates, amendments, reportable adverse events, etc. Protocol/consent modifications and IB updates will be forwarded electronically to the secondary sites within 4 weeks of obtaining Washington University IRB approval. Activated secondary sites are expected to submit protocol/consent/IB modifications to their local IRBs within 4 weeks of receipt unless otherwise noted. Upon the secondary sites obtaining local IRB approval, documentation of such shall be sent to the Washington University study team within 2 weeks of receipt of approval.

Documentation of participating sites' IRB approval of annual continuing reviews, protocol amendments or revisions, all SAE reports, and all protocol violations/deviations/exceptions must be kept on file at Washington University.

The investigator or a designee from each institution must participate in a regular conference call to update and inform regarding the progress of the trial.

APPENDIX A: Karnofsky Performance Status Scale

Able to carry on normal activity and to work; no special care needed.	100	Normal no complaints; no evidence of disease.
	90	Able to carry on normal activity; minor signs or symptoms of disease.
	80	Normal activity with effort; some signs or symptoms of disease.
Unable to work; able to live at home and care for most personal needs; varying amount of assistance needed.	70	Cares for self; unable to carry on normal activity or to do active work.
	60	Requires occasional assistance, but is able to care for most of his personal needs.
	50	Requires considerable assistance and frequent medical care.
Unable to care for self; requires equivalent of institutional or hospital care; disease may be progressing rapidly.	40	Disable; requires special care and assistance.
	30	Severely disabled; hospital admission is indicated although death not imminent.
	20	Very sick; hospital admission necessary; active supportive treatment necessary.
	10	Moribund; fatal processes progressing rapidly.
	0	Dead

APPENDIX B: PATIENT'S MEDICATION DIARY

Today's Date: _____

Agent: _____

Cycle: _____

Patient Name: _____

Study ID#: _____

INSTRUCTIONS TO THE PATIENT:

1. Complete one form for each month. Take 20 mg (2 capsules) of lenvatinib daily at approximately the same time each day. Take the lenvatinib with a glass of water and drink the glass of water in as little time as possible. Swallow the capsules whole and do not chew the capsules.
2. Record the date, the number of capsules taken, and when you took them.
3. If you forgot to take your lenvatinib dose and it cannot be taken within 12 hours of the normal dosing time within the same day, then do not take a dose that day. Restart taking the lenvatinib the next day.
4. If you have any questions or notice any side effects, please record them in the comments section. Record the time if you should vomit.
5. Please return the forms to your physician or your study coordinator when you go to your next appointment. Please bring your unused study medications and/or empty bottles with you to each clinic visit so that a pill count can be done.
6. Avoid St. John's Wort, Seville oranges, grapefruit, grapefruit juice, grapefruit hybrids, pummelos, and exotic citrus fruits from 7 days before you start taking lenvatinib and throughout the entire study.

Day	Date	What time was dose taken?	# of tablets taken	Comments
1				
2				
3				
4				
5				
6				
7				
8				
9				
10				
11				
12				
13				
14				
15				
16				
17				
18				
19				
20				
21				

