1.0 SCHEDULE OF ACTIVITIES

Screening tests may take place no more than 21 days prior to the first day of study treatment. Window for study visits during treatment is +/- 7 days.

	Screening	C1D1	D1 of each subsequent cycle	Q9 wks	EOT	FU ⁴
Informed consent	X					
H&P, PS	X					
Vital signs	X		X			
CBC	X	X	X		X	
Blood chemistry ⁹	X		X			
Pregnancy test ¹	X ³					
TSH	X		X			
INR	X		X			
Urinalysis	X					
UPCR		X	X			
ECG	X					
CT or MRI ⁸	X			X	X	
Pembrolizumab		X	X			
Lenvatinib ²		X-----X ²				
Research tissue collection ⁷	X					
Research blood collection	X ⁵	X ⁵	X ⁶		X	
Adverse events	X-----X					
Progression and survival						X

1. Women of childbearing potential only
2. Lenvatinib is to be self-administered daily on each day of every 21-day cycle
3. Within 72 hours prior to first dose
4. After coming off treatment, patients will be followed every 12 weeks +/- 1 week until death for survival. If patients discontinue treatment prior to progression, patients will continue to be followed by scans approximately every 9 weeks until progression or the start of another anti-cancer therapy.
5. To be drawn at screening or C1D1 (up to 14 days prior to the start of treatment)
6. C4D1 only
7. Archival from within 3 months (preferred), up to 6 months acceptable; if no biopsy has been performed in the 6 months prior to treatment start then an SOC biopsy should take place after a patient has been determined to be eligible for the trial, if safe and feasible. See section 10.0 for more details.
8. Scans should continue every 9 weeks regardless of cycle length. See Section 12 for further instructions of timelines for obtaining confirmatory scans. For responses, or progression, a confirmatory scan should be performed at least 4 weeks after the initial scan showing progression or response.
9. Albumin, alkaline phosphatase, total bilirubin (and direct bilirubin if total bilirubin is above ULN), bicarbonate, BUN, calcium, chloride, creatinine, glucose, phosphorus, potassium, total protein, AST, ALT, sodium

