7.1 Lenvatinib

Lenvatinib dose reduction and interruption for subjects who experience lenvatinib-related toxicity will be in accordance with the dose reduction instructions shown in the tables below. Any dose reduction below 4 mg/day must be discussed with the trial PI. Once the dose has been reduced, it cannot be increased at a later date.

Dose Reduction Recommendations for Lenvatinib Treatment-Related Toxicity

Initial Lenvatinib Dose	Adjusted Dose To Be Administered			
	Reduction 1	Reduction 2	Reduction 3	Reduction 4
20 mg QD	14 mg QD	10 mg QD	8 mg QD	4 ^a mg QD

a. Consult trial PI for further dose reduction recommendations.

Occurrence of Lenvatinib Treatment-related Toxicity^{a,b}	During Therapy		Adjusted Dose^f
	Grade 1, Tolerable Grade 2		
Any occurrence	Continue treatment		No change
Intolerable Grade 2^{c,d} and Grade 3^g			
First occurrence	Interrupt lenvatinib until resolved to tolerable Grade 2, or Grade 0-1		Reduce lenvatinib by 1 dose level

Second occurrence (same toxicity or new toxicity)	Interrupt lenvatinib until resolved to tolerable Grade 2, or Grade 0-1	Reduce lenvatinib by 1 more dose level
Third occurrence (same toxicity or new toxicity)	Interrupt lenvatinib until resolved to tolerable Grade 2, or Grade 0-1	Reduce lenvatinib by 1 more dose level
Fourth occurrence (same toxicity or new toxicity)	Interrupt lenvatinib until resolved to tolerable Grade 2, or Grade 0-1	Reduce lenvatinib by 1 more dose level
Grade 4^{e,g}		
Any occurrence	Discontinue lenvatinib	

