9.1.5 Dosage Form and Preparation

E7080 drug products used in clinical studies are hard capsules containing 1, 4, or 10 mg E7080 as anhydrous free base. The size of the capsules is No. 4 for all strengths with an average length of 14.3 mm. The color of the cap is yellowish-red for all strengths. The colors of the body are white, yellowish-red, and yellow for the 1-mg, 4-mg, and 10-mg strengths, respectively (capsules with or without markings in black ink might be used).

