9.1.7 Administration

Lenvatinib will be given at a dose of 20 mg (two 10 mg capsules) once daily. The daily dose of lenvatinib is to be modified as needed according to the dose/toxicity management plan.

Lenvatinib is to be taken at the same time each day with or without food.

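### The patient's lenvatinib diary prints a fixed 20 mg dose that is wrong after any dose reduction

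*Combined protocol and SAP*

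**What the plan says.** Appendix B is the diary the patient takes home. Its first instruction reads "Complete one form for each month. Take 20 mg (2 capsules) of lenvatinib daily at approximately the same time each day", and its second reads "Record the date, the number of capsules taken, and when you took them". The header asks for today's date, agent, cycle, patient name and study number. The table has rows for days 1 to 21 and columns for day, date, time of dose, number "of tablets taken" and comments. There is no field for the assigned dose and none for capsule strength.

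Section 7.1 plans for the dose to fall: "Lenvatinib dose reduction and interruption for subjects who experience lenvatinib-related toxicity will be in accordance with the dose reduction instructions shown in the tables below". The levels after 20 mg are 14, 10, 8 and 4 mg once daily, and "Once the dose has been reduced, it cannot be increased at a later date". Section 9.1.7 gives the same 20 mg starting dose as two 10 mg capsules but goes on to say "The daily dose of lenvatinib is to be modified as needed according to the dose/toxicity management plan". The product comes as "hard capsules containing 1, 4, or 10 mg E7080 as anhydrous free base" (Section 9.1.5). The footnote on lenvatinib in the Schedule of Activities sets the dosing period: "Lenvatinib is to be self-administered daily on each day of every 21-day cycle".

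**The concern.** The diary is a written dosing instruction in the patient's hands. It is right on day 1 and becomes wrong when the dose is first reduced. Because reductions are permanent, it stays wrong for the rest of that patient's treatment. It lacks the modification clause that Section 9.1.7 carries, and nothing in the documents tells sites to amend it or to issue another version.

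The patients affected are those who have already had lenvatinib toxicity, and where the instruction misleads, it points to a higher dose than the one assigned. Reductions are a planned route: Section 7.1 calls for one at each Grade 3 or intolerable Grade 2 lenvatinib-related event, with listed exceptions. In the earlier study of the same two doses summarised in Section 2.5, 21 of 30 patients (70%) had Grade 3 or 4 adverse events. That is not a reduction rate, but it suggests reductions will not be rare.

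A secondary matter is the dose record. A count without strength does not show what was taken once more than one strength is in use. Lenvatinib exposure bears on the per-protocol set in Section 15.5, which requires at least 80% of the targeted dosage and is used for sensitivity analyses.

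**Working it through.** **Inputs.** Printed instruction: 20 mg, 2 capsules daily (Appendix B). Dose levels: 20, 14, 10, 8 and 4 mg (Section 7.1). Capsule strengths: 1, 4 and 10 mg (Section 9.1.5). Cycle length: 21 days (Schedule of Activities; Section 6.1). Assumption: the pharmacy dispenses the fewest capsules that make up the dose. The documents do not say this.

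**The diary's own figure.** 2 × 10 mg = 20 mg. This reproduces, and it holds for the starting dose only.

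**Effect of taking two capsules at each level.** The ratio is (mg in two capsules from the dispensed supply) / (assigned mg).

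| Assigned dose | Fewest capsules | Two capsules give | Share of assigned dose |
|---|---|---|---|
| 20 mg | 10 + 10 (2) | 20 mg | 20/20 = 100% |
| 14 mg | 10 + 4 (2) | 14 mg | 14/14 = 100% |
| 10 mg | 10 (1) | 20 mg | 20/10 = 200% |
| 8 mg | 4 + 4 (2) | 8 mg | 8/8 = 100% |
| 4 mg | 4 (1) | 8 mg | 8/4 = 200% |

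**Effect of following the printed mg.**
- At 10 mg, the printed mg and the printed count agree with each other (2 × 10 mg), so either one leads to 200%.
- At 14 mg, the 10 mg capsules in hand allow 2 × 10 mg: 20/14 = 143%.
- At 8 and 4 mg, reaching 20 mg from 4 mg capsules would take 20/4 = 5 capsules, against the printed count of two. I do not count that case, nor any that needs leftover capsules of another strength.

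**How long an error could run.** If exactly 21 ten-mg capsules are dispensed for a cycle at the 10 mg level (a further assumption), two a day exhausts them in 21/2 = 10.5 days. Early run-out or the pill count would then reveal the error, but only after the extra doses had been taken.

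**What a recorded count identifies.** From the table, an entry of 2 fits 20, 14 or 8 mg, and an entry of 1 fits 10 or 4 mg.

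**Month against cycle.** The form has 21 rows. Used once per calendar month, it leaves 28 − 21 = 7 to 31 − 21 = 10 days without a row.

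**The case against.** The strongest reply is that this is a starting-dose form, correct for every patient until a reduction, and that Section 7.1 governs afterwards. A patient just told of a reduction would have to follow pre-printed text over the investigator's instruction. By count, the form is harmless at two of the four reduced levels. In none of the scenarios above does the daily dose exceed 20 mg, the starting dose.

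There are also safeguards. Patients bring unused medication and empty bottles to each visit for a pill count, visits fall on day 1 of each 21-day cycle, the Treatment Form is due every cycle (Section 11.0), and the three strengths have different body colours (Section 9.1.5). The monthly wording is offset by the Cycle field, the 21 rows and the instruction to return forms at the next appointment. No section names the diary as the source for dose analysis.

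Much of this stands, and it limits the size of the problem. The month-versus-cycle and strength points are minor, and other records may well recover the dose. What it does not answer is the printed instruction itself. The pill count and the Treatment Form detect an error only after doses are taken. A ceiling of 20 mg is little comfort for a patient who could not tolerate 20 mg. Nor would a doubled reduced dose be caught by overdose reporting, since Appendix C sets the lenvatinib threshold at 120 mg. Bottle labels or site counselling may correct the instruction, but they are not in the documents.

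**Conclusion.** The concern holds. The diary states a mg dose that conflicts with Section 7.1 at 14, 10, 8 and 4 mg, and nothing in the documents supplies a corrected form. That rests on the text alone.

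The size of a possible dosing error rests on fewest-capsule dispensing and on a patient following the form: 200% of the assigned dose at 10 and 4 mg, 143% at 14 mg if the printed mg is followed, and no excess by count at 14 and 8 mg. The documents do not give the share of patients reaching each level, so no number of affected patients can be stated.

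At reduced doses the diary alone does not document the dose taken. The monthly wording is a small inconsistency. The primary response-rate test, its alpha and power, and the sample size are untouched. This should be fixed because it is a wrong patient-facing instruction that is cheap to correct, not because it threatens the trial's conclusion.

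**What to change.** Revise Appendix B in three places:

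1. Replace the printed 20 mg (2 capsules) with a line the site completes each cycle and re-issues at every dose change: *Your current dose: __ mg = __ × 10 mg + __ × 4 mg + __ × 1 mg capsules.*
2. Describe the form as one per 21-day cycle instead of one per month.
3. Replace the tablet count with capsules taken by strength, or total mg taken.

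The first change matters most and would be worth making alone. The cost is a one-page form revision with IRB approval, plus a short entry by site staff each cycle. No dose level and no analysis changes.

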APPENDIX C: Definitions for Adverse Event Reporting

A. Adverse Events (AEs)

As defined in 21 CFR 312.32:

Definition: any untoward medical occurrence associated with the use of a drug in humans, whether or not considered drug-related.

Grading: the descriptions and grading scales found in the revised NCI Common Terminology Criteria for Adverse Events (CTCAE) version 5.0 will be utilized for all toxicity reporting. A copy of the CTCAE version 5.0 can be downloaded from the CTEP website.

Attribution (relatedness), Expectedness, and Seriousness: the definitions for the terms listed that should be used are those provided by the Department of Health and Human Services' Office for Human Research Protections (OHRP). A copy of this guidance can be found on OHRP's website:

<http://www.hhs.gov/ohrp/policy/advevntguid.html>

B. Suspected Adverse Reaction (SAR)

As defined in 21 CFR 312.32:

Definition: any adverse event for which there is a reasonable possibility that the drug caused the adverse event. "Reasonable possibility" means there is evidence to suggest a causal relationship between the drug and the adverse event. "Suspected adverse reaction" implies a lesser degree of certainty about causality than adverse reaction, which means any adverse event caused by a drug.

C. Life-Threatening Adverse Event / Life Threatening Suspected Adverse Reaction

As defined in 21 CFR 312.32:

Definition: any adverse drug event or suspected adverse reaction is considered "life-threatening" if, in the view of the investigator, its occurrence places the patient at immediate risk of death. It does not include an adverse event or suspected adverse reaction that, had it occurred in a more severe form, might have caused death.

D. Serious Adverse Event (SAE) or Serious Suspected Adverse Reaction

As defined in 21 CFR 312.32:

Definition: an adverse event or suspected adverse reaction is considered "serious" if, in the view of the investigator, it results in any of the following outcomes:

- Death
- A life-threatening adverse event

- Inpatient hospitalization or prolongation of existing hospitalization
- A persistent or significant incapacity or substantial disruption of the ability to conduct normal life functions
- A congenital anomaly/birth defect
- A new cancer (that is not a condition of the study)
- Associated with an overdose
- Any other important medical event that does not fit the criteria above but, based upon appropriate medical judgment, may jeopardize the subject and may require medical or surgical intervention to prevent one of the outcomes listed above

E. Protocol Exceptions

Definition: A planned change in the conduct of the research for one participant.

F. Deviation

Definition: Any alteration or modification to the IRB-approved research without prospective IRB approval. The term “research” encompasses all IRB-approved materials and documents including the detailed protocol, IRB application, consent form, recruitment materials, questionnaires/data collection forms, and any other information relating to the research study.

A minor or administrative deviation is one that does not have the potential to negatively impact the rights, safety, or welfare of participants or others or the scientific validity of the study.

A major deviation is one that does have the potential to negatively impact the rights, safety, or welfare of participants or others or the scientific validity of the study.

G. Overdose

Definition: For purposes of this trial, an overdose of pembrolizumab will be defined as any dose of 1,000 mg or greater (≥ 5 times the indicated dose). No specific information is available on the treatment of overdose of pembrolizumab. In the event of overdose, the subject should be observed closely for signs of toxicity. Appropriate supportive treatment should be provided if clinically indicated.

An overdose of lenvatinib will be defined as any dose of 120 mg or greater (≥ 6 times the indicated dose). There is no specific antidote for overdose with lenvatinib. In case of suspected overdose, lenvatinib should be withheld and supportive care initiated.

H. Events of Clinical Interest

Events of clinical interest for this trial include:

1. an overdose of Merck product (either pembrolizumab or lenvatinib), as defined in Section 8.6.1 - Definition of an Overdose for This Protocol and Reporting of Overdose to the Sponsor, that is not associated with clinical symptoms or abnormal laboratory

results.

2. an elevated AST or ALT lab value that is greater than or equal to 3X the upper limit of normal and an elevated total bilirubin lab value that is greater than or equal to 2X the upper limit of normal and, at the same time, an alkaline phosphatase lab value that is less than 2X the upper limit of normal, as determined by way of protocol-specified laboratory testing or unscheduled laboratory testing.*

***Note:** These criteria are based upon available regulatory guidance documents. The purpose of the criteria is to specify a threshold of abnormal hepatic tests that may require an additional evaluation for an underlying etiology.

APPENDIX D: Reporting Timelines

Expedited Reporting Timelines			
Event	HRPO	QASMC	Merck
Serious adverse event			Report within 2 working days.
Unanticipated problem involving risk to participants or others	Report within 10 working days. If the event results in the death of a participant enrolled at WU/BJH/SLCH, report within 1 working day.	Report via email after IRB acknowledgment	
Overdose			If an AE is associated with overdose of either pembrolizumab or lenvatinib, report as a serious adverse event within 2 working days. If an overdose is taken without any associated AE, report as a non-serious Event of Clinical Interest to Merck within 2 working days.
Pregnancy and infant exposure during breastfeeding			Report within 2 working days.
Event of Clinical Interest			Report within 2 working days.
Major deviation	Report within 10 working days. If the event results in the death of a participant enrolled at WU/BJH/SLCH, report within 1 working day.		
A series of minor deviations that are being reported as a continuing noncompliance	Report within 10 working days.		
Protocol exception	Approval must be obtained prior to implementing the change		
Complaints	If the complaint reveals an unanticipated problem involving risks to participants or others OR noncompliance, report within 10 working days.		

Expedited Reporting Timelines			
Event	HRPO	QASMC	Merck
	If the event results in the death of a participant enrolled at WU/BJH/SLCH, report within 1 working day. Otherwise, report at the time of continuing review.		
Breach of confidentiality	Within 10 working days.		
Incarceration	If withdrawing the participant poses a safety issue, report within 10 working days. If withdrawing the participant does not represent a safety issue and the patient will be withdrawn, report at continuing review.		

Routine Reporting Timelines			
Event	HRPO	QASMC	Merck
Adverse event or SAE that does not require expedited reporting	If they do not meet the definition of an unanticipated problem involving risks to participants or others, report summary information at the time of continuing review	Adverse events will be reported in the toxicity table in the DSM report which is typically due every 6 months.	
Minor deviation	Report summary information at the time of continuing review.		
Complaints	If the complaint reveals an unanticipated problem involving risks to participants or others OR noncompliance, report within 10 working days. If the event results in the death of a participant enrolled at WU/BJH/SLCH, report within 1 working day. Otherwise, report at the time of continuing review.		
Incarceration	If withdrawing the participant poses a safety issue, report within 10 working days. If withdrawing the participant does not represent a safety issue and the patient will be withdrawn, report at continuing review.		

Expedited Reporting Timelines for Secondary Sites			
Event	WU (Coordinating Center)	Local IRB	Merck
Serious AND unexpected suspected adverse reaction	Report no later than 11 calendar days after it is determined that the information qualifies for reporting.	Report all applicable events to local IRB according to local institutional guidelines.	The research team at Washington University is responsible for reporting all applicable events to Merck as needed.
Unexpected fatal or life-threatening suspected adverse reaction	Report no later than 4 calendar days after initial receipt of the information.		
Unanticipated problem involving risk to participants or others	Report no later than 4 calendar days after initial receipt of the information.		
Overdose	Report within 24 hours.		
Event of Clinical Interest	Report within 24 hours.		
Pregnancy and infant exposure during breastfeeding	Report within 24 hours.		
Adverse event or SAE that does not require expedited reporting	As per routine data entry expectations		
Protocol exception	Approval must be obtained prior to implementing the change.		

